The primary end point will be the frequency of patients who experience an excellent tolerability along with a decrease of at least 20% in pain score. Also pain score and opioid consumption will be compared to data obtained 5 consecutive who underwent a C-section the month before.

Specific Aims

Specific Aims:

1. Tolerability and feasibility of applying the device following Cesarean Section
2. Look at the trend of opioid consumption and pain in five post- Cesarean section women wearing device, compared to five historical consecutive controls of women who underwent cesarean section in January 2019

Study Design

The proposed pilot study will be conducted as a single-center prospective open-label trial at the University of Pittsburgh Medical Center (UPMC) Magee-Womens Hospital. The data collected during this period will be compared to historical controls who have had elective C-Sections in the period of January, 2019. Institutional review board approval will be obtained before eligible patients are recruited and consented. Trial will be registered at www.clinicaltrials.gov before beginning recruitment.

Recruitment

Potential subjects will be recruited in the Magee Womens Hospital obstetrical unit when they arrive for elective Cesarean Section surgery. The Principal Investigator, [name] [name], will already have access to these patients as their primary OB Anesthesiologist. Patients will be asked for their interest in pursuing a research study that involves wearing a percutaneous, auricular field stimulator for five days as a supplementary method of post-operative pain control after their Cesarean-Section. Patients who agree to participate in the trial will sign an IRB approved Informed Consent Form.

Inclusion Criteria:

Over 18 years of age

Elective Cesarean-Section Surgery

Exclusion Criteria:

History of active depression, anxiety or catastrophizing

Active alcoholism or drug abuse

Severe chronic pain condition that requires daily preoperative opioid dependence

History of hemophilia

Patients with cardiac pacemakers

Patients with psoriasis vulgaris diagnosis

Data Collection and Outcome Measures

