The primary purpose of this pilot study is to demonstrate feasibility/acceptability of the NSS-2 Bridge device applied after a C-section. If the acceptability is confirmed, the C-section model will be included in an RFA NIH request (RFA-NS-19-018: HEAL Initiative: Clinical Devices to Treat Pain (UH3 Clinical Trial Optional) DEADLINE IS MARCH 8, 2019) for proposal related to the use of devices for reduction of opioid use. In this pilot, no changes will be made in the other analgesia/postpartum care. Potential subjects will

be recruited in the Magee-Womens Hospital obstetrical unit when they arrive for cesarean delivery. Patients will be asked if they are interested in using the NSS-2 Bridge system as a way to control pain after the C-section. They will offer to review a video explaining the mechanism of action of the NSS-2 Bridge system. Subject will be informed of the purpose of this pilot evaluation and if they agree to participate in the trial, they will sign an IRB approved Informed Consent Form.

Once patient has given and signed informed consent to participate in the study, demographic information and medical history will be collected from each participant on the day of the C-section. Data will be de-indemnified and kept in a lock cabinet. The NSS-2 BRIDGE device will be applied to one ear by trained research staff in the immediate post-operative setting. The patient will be informed at the time of consent and after the implantation of the device that they can have the device removed any time after its application.

As per standard of care, at 12, 24, 48, 72, 96 and 120 hours post-operatively will be collected pain score at rest and movement, total opioid consumption, as well as the device tolerability. Additionally as per other pain pilot IRB approved projects, we shall also collect common medical information including time to bowel movement, PONV, time to oral intake (liquid and regular diet), time to hospital discharge, intensive care unit (ICU) admission, readmission to the hospital, readmission due to pain related issues, quality of recovery after cesarean delivery, overall patient satisfaction, and patient satisfaction related to pain management. When the patient is discharged from the hospital, they will be asked to complete a patient satisfaction survey. For patients discharged with the device attached, removal instructions will be given to patient to remove and dispose of the device at 120 hours.

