Standard opioid conversion table will be used to convert the oral and IV narcotic utilized by the patients to IV morphine equivalent doses (MED) for analysis purposes.

Overall patient satisfaction and satisfaction of pain management during hospitalization will be measured by a numerical rating scale with 0- worst satisfaction and 10 being the best satisfaction. The patient satisfaction test will be administered by a member of the research team.

No statistical analysis will be performed. The primary end point will be the frequency of patients who experience an excellent tolerability along with a decrease of at least 20% in pain score. Also pain score and opioid consumption will be compared to data obtained 5 consecutive who underwent a C-section the month before

Pre-and-Post Metric Evaluation

The use of a non-pharmacological NSS-2 BRIDGE has the possibility of providing analgesia to post-surgical patients and reducing the number of opioids required following Cesarean-Section surgery. This will significantly impact patient outcomes, as patients will experience fewer opioid-related side effects (such as respiratory depression, post-operative nausea and vomiting, constipation and delirium, as well as transfer of opioids to the breast milk). This will also impact clinicians caring for post-operative patients, as there is the real potential they will have fewer conditions to monitor and treat as the patient recovers from surgery. The projected number of patients served by this project will initially be five (5) enrolled participants at Magee-Womens Hospital however, the data collected from this trial will serve countless patients and the community at large as physicians strive to move away from opioid use following surgery. Data collected from this pilot study will support a future proposal to the National Institute of Health (NIH) to fund a full-scale, randomized, placebo-controlled trial using the NSS-2 BRIDGE device.

Perhaps most importantly, the investigative use of the non-invasive NSS-2 BRIDGE device has the ability to significantly increase patient satisfaction in individuals who are opioid naïve or adverse to taking opioids as a method of pain control. Being able to offer the post-partum patients at Magee

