Womens Hospital of UPMC such an alternative represents a great opportunity to increase patient satisfaction, outcomes and compliance as many patients increasingly fear the use of opioids. The NSS-2 BRIDGE will remain effective on the participant for five days, and will have lasting effects even after discharge from the hospital, which is a time when many patients turn to opioids to control pain. The way the efficacy of this device will be measured will be by comparing total perioperative opioid consumption between study participants (n=5) historical controls who have had C-Sections at Magee Womens hospital in January 2019. Other outcome measures include the incidence of respiratory depression, PONV, constipation and length of stay between the study group and historical control group.

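### The protocol says device efficacy will be measured by an opioid comparison of 5 participants with historical controls, which the design can only describe; the primary x/5 also lacks a statement of precision

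*Protocol*

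**What the plan says.** The last paragraph of Pre-and-Post Metric Evaluation states: "The way the efficacy of this device will be measured will be by comparing total perioperative opioid consumption" between study participants (n=5) and women who had a C-section at the same hospital in January 2019. That sentence gives a number for the participants only. The control group size comes from elsewhere: Aim 2 refers to "five historical consecutive controls of women who underwent cesarean section in January 2019", and Data Collection and Outcome Measures says "Also pain score and opioid consumption will be compared to data obtained 5 consecutive who underwent a C-section the month before".

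The protocol describes the aim of the study more modestly in other places:

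- Specific Aims, Aim 2: "Look at the trend of opioid consumption and pain in five post- Cesarean section women wearing device".
- Data Collection and Outcome Measures: "The primary purpose of this pilot study is to demonstrate feasibility/acceptability of the NSS-2 Bridge device applied after a C-section".
- Pre-and-Post Metric Evaluation, first paragraph: the pilot data are to support a later proposal to "fund a full-scale, randomized, placebo-controlled trial using the NSS-2 BRIDGE device".

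On analysis, Data Collection and Outcome Measures says "No statistical analysis will be performed". The next sentence defines the primary endpoint as the frequency of patients with both excellent tolerability and a fall in pain score of at least 20%. The same section makes inclusion of the C-section model in a grant request conditional on acceptability being confirmed.

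**The concern.** Two separate matters arise, and the second should not borrow weight from the first.

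The first is the efficacy wording. It gives a small comparison with historical controls a function that the design cannot perform. Since the data are meant to support a funding proposal on reducing opioid use, a difference between two groups of five could be carried forward under the label of efficacy.

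The second is precision. The result that decides whether acceptability is confirmed is a count out of five. With statistical analysis ruled out in so many words, nothing would accompany that count to show how little it pins down the underlying rate. This is not mere silence that a statistical analysis plan would fill, because the protocol itself states the rule.

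**Working it through.** **No figure to reproduce.** The protocol gives n=5 without a derivation and states no alpha, power, effect size or standard deviation.

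**Efficacy wording: can this contrast measure efficacy?** The passages on how the two groups are formed compare as follows.

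| Feature | Participants | Controls |
|---|---|---|
| Hospital | Magee-Womens | Magee-Womens |
| Period | Prospective | January 2019, the month before |
| Elective surgery | Inclusion criterion | Stated in Study Design only |
| Selection | Asked about interest in the device, then consented | Consecutive |
| Exclusion criteria | Applied | Not stated to apply |
| Other analgesia and postpartum care | Unchanged by the pilot | No device, no pilot procedures |

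Several features limit group differences: the same hospital, adjacent periods, consecutive controls and unchanged other care. Two do not.

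1. Only participants pass a filter on interest: "Patients will be asked if they are interested in using the NSS-2 Bridge system as a way to control pain".
2. Only participants are stated to be screened by the exclusion criteria. These include active depression, anxiety or catastrophizing, drug abuse, and chronic pain needing opioids every day before surgery. Such factors bear directly on pain and opioid use after surgery.

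A difference in total opioid consumption could therefore come from the device, from selection, from chance with five per group, or from any mixture. The protocol has no means of separating these. Nothing in it fixes the direction or the size of a selection effect.

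**Primary frequency: how precise is x/5?** Inputs: n=5 (Pre-and-Post Metric Evaluation). The two-sided 95% level is my assumption, since the protocol sets none. Method: exact (Clopper-Pearson) limits, where the lower limit L solves P(X ≥ x | L) = 0.025 and the upper limit U solves P(X ≤ x | U) = 0.025.

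- 5/5: L⁵ = 0.025, so L = 0.025^(1/5) = 0.478; U = 1. Interval 48% to 100%.
- 4/5: 5L⁴(1−L) + L⁵ = 0.025 gives L = 0.284; 1 − U⁵ = 0.025 gives U = 0.975^(1/5) = 0.995 (0.9949 before rounding). Interval 28% to 99%.
- 3/5: the same equations give L = 0.147 and U = 0.947. Interval 15% to 95%.

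Even a perfect result is compatible with a true rate just under one half.

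**The case against.** **The efficacy sentence may only name an outcome measure.** The sentence after it goes on to list further outcomes, no test is planned, and the protocol elsewhere limits the pilot to feasibility. This is fair, and it is why the point is about wording. A reader might infer a strict contradiction, or that the protocol otherwise treats the contrast uniformly as a trend. The text supports neither: the word trend occurs only in Aim 2, and the other mentions say that the data will be compared. What stands is that no other section calls this comparison the measure of efficacy.

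**A five-patient pilot may report x/5 descriptively.** This stands. The denominator is visible, and the no-analysis sentence may have been meant only to exclude hypothesis tests. A reader might conclude that the bare count is an error or that n=5 is a design fault; the documents support neither conclusion. The statement about one half also depends on the two-sided convention: the one-sided 95% lower limit for 5/5 is 0.05^(1/5) = 55%.

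**An interval does not define the responder.** This is also true. The protocol text gives no cut-off for excellent tolerability and no numerical threshold for confirmed acceptability. An interval addresses sampling error only and cannot repair either.

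**A precision figure for the opioid difference is tempting.** With equal SDs and roughly normal data, the 95% half-width for 5 vs 5 is 2.306 × √(2/5) = 1.46 SD. But the protocol plans no such interval and gives no SD, so the conclusion does not rest on this figure.

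**A bias in favour of the device is tempting to infer.** The filters on participants make that conceivable, but the protocol gives no data on the controls, and neither sign nor size is established.

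**Conclusion.** The point holds as a minor one. The efficacy sentence in Pre-and-Post Metric Evaluation over-claims: a non-randomised, open-label contrast of five participants with five historical controls can describe opioid use but cannot measure what the device does. This rests on how the groups are formed, not on an assumed variance. It takes the exclusion criteria as not applied to controls because no section says that they are; if they were in fact applied, the imbalance would shrink, but the filter on interest and the lack of randomisation would remain.

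The missing precision statement is an inexpensive improvement, not a fault. Its size is given by the exact intervals above, at an assumed two-sided 95% level, and by reading the no-analysis rule as excluding an interval too.

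**What to change.** 1. Pre-and-Post Metric Evaluation: replace the efficacy sentence with a statement that the comparison of total opioid consumption with historical controls is descriptive and hypothesis-generating, in line with Aim 2, and supports no conclusion on efficacy.
2. Data Collection and Outcome Measures: replace the no-analysis sentence with wording such as: *No hypothesis tests will be done. Analysis is descriptive. The primary proportion will be reported with its exact (Clopper-Pearson) 95% interval. Individual pain and opioid values will be shown by group, with a note that the controls are non-randomised and not stated to have been screened by the same exclusion criteria.*

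Cost: two wording changes and one simple calculation. The efficacy language becomes less favourable, and the interval will be wide whatever the result. Design, endpoint, sample size and data collection do not change.

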Appendix 1: NSS- 2 BRIDGE device
